6.1.2. Part B: Multiple Ascending Dose – Drug-Drug Interaction Design

Part B will comprise a double-blinded, MAD, staggered parallel design in dyslipidemic (TG: 150 to 499 mg/dL; LDL-c: 100 to 200 mg/dL), statin-free, overweight (BMI 27.0 to 40.0 kg/m²), male and female subjects investigating the safety, tolerability, and PK of multiple doses of LY3202328 and the effect of LY3202328 on simvastatin and atorvastatin exposure.

A total of 40 subjects will be enrolled and divided evenly into 4 study periods (n=10 subjects per study period) to evaluate 4 dose levels of LY3202328 (Periods 5, 6, 7, and 8 at 5, 20, 100, and 300 mg, respectively, are planned).

Within each cohort, 5 subjects will be stratified to the simvastatin DDI assessment and 5 subjects will be stratified to the atorvastatin DDI assessment. Within each stratum subjects will be randomly assigned 4:1 to receive LY3202328 or placebo so that 8 subjects will receive LY3202328 and 2 subjects receive placebo in each cohort. Subjects will receive QD dose of LY3202328 or placebo in the morning in the fasted state for 29 total days. For DDI assessment, subjects will also receive a single atorvastatin or simvastatin dose a week prior to LY3202328 treatment initiation, and on Day 29 after initiation of LY3202328 daily dosing (coadministered with LY3202328).

The dose levels intended for study in Part B may change based upon data from Part A, but will range from as low as 1 mg and are not to exceed the highest dose evaluated in Part A. Any dose level used in Part B will not start until the safety data from the same or higher dose level in Part A has been reviewed by the safety committee responsible for dose escalation decisions.

Potential subjects will be screened to assess their eligibility to enter the study within 42 days prior to study entry (i.e., prior to Check in for Part B). For each cohort, subjects will be admitted to the CRU on Day –8 (the day before administration of a single dose of simvastatin or atorvastatin) and will be discharged 24 hours postdose (Day –6).

Subjects will be confined to the CRU from Day –2 to Day 2 (48 hours postdose) for initial dosing with LY3202328 and are required to return to the CRU for dosing and PK sampling the mornings of Days 7, 14, and 21. Prior to discharge from the CRU on Day 2, subjects will receive a labeled container with doses of LY3202328 that subjects will self-administer daily at home until the next morning visit at the CRU. Subjects will be instructed to take the drug QD in the morning in the fasted state and wait at least 60 minutes after the completion of dosing prior to commencing their breakfast. Subjects will be given diaries to record the time of their self-administered doses, whether the dose was administered with food or fasted, and the time of commencing the breakfast meal. Subjects must return the container (empty or not) and their diary at the next morning visit. Home dosing will be monitored via attempted phone calls when subjects will be reminded to take their medication and queried about the occurrence of AEs. Subjects should be instructed to take their dose at approximately the same time they received their first dose. Subjects will again be confined to the CRU on Day 27 (2 days before coadministration of LY3202328 or placebo with simvastatin or atorvastatin on Day 29) to Day 30 (24 hours post-coadministration of LY3202328 or placebo with simvastatin or

atorvastatin). Subjects will return to the CRU on Days 35 and 56 (168 and 672 hours postdose, respectively) for follow-up assessments.

The dose levels intended for study in Part B will be within the range of those tested in Part A. Specific dose levels will be selected after review of Part A data. Doses may range up to 300 mg or the maximum tolerated dose established in SAD Part A.

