6.1. Overall Design

Study I8Q-MC-GSEA (GSEA) is a first-in-man, Phase 1, randomized, double-blind, placebo-controlled, 2-part, ascending single- and multiple-oral dose study of LY3202328 in statin-free, overweight, healthy subjects (Part A) and in statin-free, overweight, dyslipidemic subjects with a statin DDI assessments (Part B).

This study will be conducted in 2 parts: Part A, a SAD study design at a single site and Part B, a MAD study design conducted in multiple sites.

Figure GSEA.1 illustrates the study design.

Part A: Single Ascending Dose

Cohort	N	Week								
		1	2	3	4	5	6	7	8	9
		Period 1		Period 2		Period 3			Period 4 (Food Effect)	
1	3	1 mg LY		10 mg LY		Placebo	D/C ^a			
	3	1 mg LY		Placebo		100 mg LY	D/C ^a			
	3	Placebo		10 mg LY		100 mg LY	D/C ^a			
2	3		3 mg LY		30 mg LY		Placebo		30 mg LY ^b	D/C ^a
	3		3 mg LY		Placebo		300 mg LY		Placebo ^b	D/C ^a
	3		Placebo		30 mg LY		300 mg LY		30 mg LY ^b	D/C ^a

Part B: Multiple Ascending Dose

Cohort	N	Week													
		3	4	5	6	7	8	9	10	11	12	13	14		
3	10	Period 5													
		SS/AS ^c	5 mg LY or placebo ^d	SS/AS + 5 mg LY or placebo ^e	D/C ^f										
4	10										Period 6				
		SS/AS ^c	20 mg LY or placebo ^d	SS/AS + 20 mg LY or placebo ^e	D/C ^f										
5	10										Period 7				
		SS/AS ^c	100 mg LY or placebo ^d	SS/AS + 100 mg LY or placebo ^e	D/C ^f										
6	10										Period 8				
		SS/AS ^c	300 mg LY or placebo ^d	SS/AS + 300 mg LY or placebo ^e	D/C ^f										

Abbreviations: AS = atorvastatin; CRU = clinical research unit; D/C = discharge (from the CRU); LY = LY3202328; N = number of subjects; SS = simvastatin.

- a Discharge from the CRU will occur on Day 2 with Follow-up visits to occur on Days 3 and 5.
- b LY3202328 or placebo will be administered with food.
- c A single dose of simvastatin or atorvastatin will be administered on Day -7.
- d Multiple doses of LY3202328 or placebo will be administered daily on Days 1 through 28.
- e LY3202328 or placebo will be coadministered with simvastatin or atorvastatin on Day 29.
- f Discharge from the CRU will occur on Day 30 with Follow-up visits to occur on Days 35 and 56.

Note: The doses for Part B are subject to change and will not exceed the maximum tolerated dose from Part A (starting as low as 5 mg and not to exceed 300 mg).

Figure GSEA.1. Study design for Protocol I8Q-MC-GSEA.

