6.5. Justification for Dose

Human PK/PD modeling and preclinical absorption, disposition, metabolism, and excretion (ADME) profiles in rat, dog, and primate were used to predict that LY3202328 should achieve a sustained average ED₈₀ concentration in man with an oral dose of 13 mg QD. This projected human dose compares favorably with the projected maximum absorbable dose of 190 mg determined using GastroPlus modelling of rat, dog, and monkey ADME profiles. In chronic lipid lowering studies, LY3202328 produced dose-dependent inhibition of LDL-c (61%), ApoB (53%), ApoC3 (43%), and PCSK9 (55%) in plasma, as well as liver TG (37%) in LDLr KO mice, and reduced liver TG (56%) in C57Bl/6 mice on a high fat diet. Finally, body surface area dose and predicted AUC exposure multiples are greater than 195x in GLP rat and dog toxicology studies relative to the predicted efficacy dose/exposure, and greater than 13x relative to the highest planned human dose of 300 mg. The proposed dose range for this first-in man-study of 1 to 300 mg of LY3202328 administered orally QD for up to 28 days was selected based on toxicology studies and modeling of PK/PD data from nonclinical studies of LY3202328, and the established margin of safety.

The nonclinical no-observed-adverse-effect level (NOAEL) doses and AUC values for LY3202328 following daily administration compared with planned human doses and projected human exposures are presented in [Table GSEA.1](#).

Table GSEA.1. Margin of Safety for Oral Administration of LY3202328 Based on Administered Dose and Predicted Exposure

	Dose (mg)	Dose (mg/kg)	HED (mg/kg)	Dose Multiple ^a	AUC ($\mu\text{g}\cdot\text{h}/\text{mL}$) ^b	Exposure Multiple ^a
Human^c				—	—	—
Starting dose	1	0.0143	0.0143		0.6	
Efficacy dose	13	0.186	0.186		7.8	
Highest dose	300	4.29	4.29		114	
Rat NOAEL^d		500	80.6		1710	
Starting dose				5600x		2850x
Efficacy dose				433x		219x
Highest dose				19x		15x
Dog NOAEL^e	250	139			1520	
Starting dose				9700x		2533x
Efficacy dose				747x		195x
Highest dose				32x		13x

Abbreviations: AUC = area under the plasma concentration x time curve; HED = human equivalent dose based on body surface area; NOAEL = no-observed-adverse-effect level.

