8.3.1. Dose Decision/Escalation

By nature of being a dose-escalation study, data will be evaluated on an ongoing basis until the maximum tolerated dose (MTD) is determined. The highest dose level that is tolerated will be designated as the MTD. Doses in Part B will not exceed the MTD dose determined in Part A.

Safety data will be the primary criteria for the dose escalation. Dose escalation cannot occur without prior discussion and agreement between the investigator and the Chorus CRP.

Safety data, in particular AEs, serious adverse events (SAEs), and adverse laboratory abnormalities, will be independently assessed by the investigator, and will be considered related to the investigational product unless there is clear evidence that the event is not related.

After review of these data, an agreement on the appropriate dose escalation will be made by the investigator and sponsor for the next cohort. The magnitude of the dose escalation may be

reduced following DRM, but subsequent escalations cannot be increased by more than approximately 3 fold (a half-log increment).

For dose escalation decisions safety data from at least 6 subjects completing Day 5 procedures from each dosing period in Part A will be reviewed prior to escalating to the next dosing level. For Part B, safety data from at least 8 subjects completing Day 14 safety procedures will be reviewed prior to escalating to the next dosing level.

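### The upper limit for Part B repeat dosing is stated in four ways, which diverge if the optional 600 mg dose is given in Part A or if Part A's top dose is not tolerated

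*Protocol*

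**What the plan says.** The protocol states the Part B ceiling in four forms:

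- **Section 6.1.2, fourth paragraph:** dose levels may change after Part A but "will range from as low as 1 mg and are not to exceed the highest dose evaluated in Part A". The reference point is the dose *evaluated*, not the dose tolerated.
- **Section 6.1, note to Figure GSEA.1:** doses are subject to change and are bounded by the Part A MTD, with the bracket "starting as low as 5 mg and not to exceed 300 mg".
- **Section 6.1.2, last paragraph, repeated in the synopsis under Treatment Arms:** "Doses may range up to 300 mg or the maximum tolerated dose established in SAD Part A".
- **Section 8.3.1:** "Doses in Part B will not exceed the MTD dose determined in Part A". The MTD is defined just before: "The highest dose level that is tolerated will be designated as the MTD". No 300 mg cap is repeated here.

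Part A plans single doses of 1 to 300 mg. It also reserves a 600 mg level, to be used only if exposure is still rising from 100 to 300 mg and safety supports it (synopsis; Sections 6.1.1, 11.1 and 11.3.4; SAP 2.1 and 2.2.2).

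The planned Part B doses are 5, 20, 100 and 300 mg throughout. The benefit/risk statement (Section 4.3) covers 1 to 300 mg, and the margins in Table GSEA.1 (Section 6.5) end at 300 mg.

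Two smaller differences sit beside these. The floor is 1 mg in Section 6.1.2 and 5 mg in the figure note. Section 6.5 justifies the dose range "administered orally QD for up to 28 days", while Section 6.1.2 prescribes daily dosing "in the morning in the fasted state for 29 total days".

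**The concern.** The ceiling on repeated dosing is a safety limit in a first-in-human study, and the people who set each cohort's dose need one rule. The four statements use different reference points: the top dose evaluated, the MTD alone, the MTD together with 300 mg, and 300 mg or the MTD. They agree while Part A stops at a tolerated 300 mg. They can part company if Part A goes to 600 mg, or if its top dose is not tolerated. In the first case the wording could be read to reach a dose for which the protocol presents no margin. In the second, one sentence read alone would leave available a dose that the other sections rule out.

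**Working it through.** **1. What each statement implies.** The ceiling for Part B is read from each statement on its own. In the last row, 100 mg serves as the MTD because it is the Part A level below 300 mg.

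| Part A outcome | 6.1.2, fourth paragraph (top dose evaluated) | Figure GSEA.1 note (MTD and 300 mg) | 6.1.2 end and synopsis (300 mg or MTD) | 8.3.1 (MTD) |
|---|---|---|---|---|
| 600 mg given and tolerated | 600 | 300 | 300 or 600 | 600 |
| 600 mg given, not tolerated; 300 mg tolerated | 600 | 300 | 300 | 300 |
| 600 mg not given; 300 mg tolerated | 300 | 300 | 300 | 300 |
| 600 mg not given; 300 mg not tolerated, MTD 100 mg | 300 | 100 | 300 or 100 | 100 |

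The statements agree in the third row only. The gap in the first row is 600/300 = 2-fold.

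**2. Is the 600 mg branch remote?** Table GSEA.1 predicts an AUC of 0.6 µg·h/mL at 1 mg and 7.8 at 13 mg, which is 7.8/13 = 0.6 per mg. Assuming linearity up to the predicted maximum absorbable dose of 190 mg, 100 mg gives 100 × 0.6 = 60, against the tabulated 114 at 300 mg. These are repeat-dose predictions. On them, exposure does rise from 100 to 300 mg, so the exposure condition for 600 mg would be met. The safety condition cannot be predicted.

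**3. The stated margins at 300 mg.** Inputs from Table GSEA.1: human equivalent dose 80.6 mg/kg (rat) and 139 mg/kg (dog); animal AUC 1710 and 1520; 70 kg human; predicted human AUC 114.

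- Human dose: 300/70 = 4.29 mg/kg.
- Dose multiple: 80.6/4.29 = 18.8 (stated 19x); 139/4.29 = 32.4 (stated 32x).
- Exposure multiple: 1710/114 = 15.0 (stated 15x); 1520/114 = 13.3 (stated 13x).
- The human AUC reproduces as 190 × 0.6 = 114.

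**4. The same method at 600 mg, for scale only.** The documents give no such figures.

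- Human dose: 600/70 = 8.57 mg/kg.
- Dose multiple: 80.6/8.57 = 9.4 (rat); 139/8.57 = 16.2 (dog), half of those at 300 mg.
- Exposure multiple if the 190 mg absorption limit holds: unchanged at 15.0 and 13.3.
- Exposure multiple if exposure were linear in dose (an assumption, the other end of the range): AUC = 600 × 0.6 = 360; 1710/360 = 4.8 (rat); 1520/360 = 4.2 (dog).

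**5. Duration.** Figure GSEA.1 notes d and e give Days 1 to 28 plus Day 29: 28 + 1 = 29 doses. The synopsis and Sections 6.1.2 and 8.1 agree. Only the rationale sentence in Section 6.5 says 28.

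**The case against.** A reader might infer that the protocol both allows and forbids repeat dosing above 300 mg. The documents do not support that as a flat statement. Three of the four forms are upper limits, and upper limits can all be obeyed at once; doing so gives 300 mg, or the MTD if lower. No passage names a Part B dose above 300 mg, and every list of planned Part B doses ends there. The divergence above 300 mg needs the optional 600 mg dose to be given, and under the MTD wording tolerated.

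There are also procedural safeguards. Dose levels are agreed between the investigator and the sponsor's physician at a data review meeting, and no Part B dose starts before Part A safety data at the same or a higher dose have been reviewed. Site staff do not pick a ceiling from a page.

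Much of this stands, and it is why the point is conditional. It does not remove the point. No text says that the strictest limit governs. The *or* in the synopsis and at the end of Section 6.1.2 does not say whether the lower or the higher applies. Section 6.1.2 refers to the dose evaluated where Section 8.3.1 and the figure note refer to the MTD. The safeguards govern how a decision is reached, not which written limit binds it; a reviewed 600 mg level would satisfy the same-or-higher requirement.

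It is also tempting to let the floor and the duration add weight. They should not. A 1 mg dose lies inside the Part A range, and the duration gap is one day in one rationale sentence. A claim that 28-day animal studies cannot support a 29th dose would need a standard that the documents do not give.

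**Conclusion.** The ceiling for Part B repeat dosing is inconsistent as written. The practical effect is conditional:

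- **600 mg given and tolerated in Part A:** the ceiling is 600 mg under Section 6.1.2 (fourth paragraph) and Section 8.3.1, 300 mg under the figure note, and undetermined between the two in the synopsis and at the end of Section 6.1.2.
- **Top evaluated dose not tolerated:** the fourth paragraph of Section 6.1.2, read alone, is looser than the MTD limit in Section 8.3.1 and the figure note.
- **Part A ends at a tolerated 300 mg:** all statements agree, and the planned doses fit every version.

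This rests on reading each statement by itself, since no order of precedence is given. No margin is stated above 300 mg; the 600 mg multiples under working show scale only, and their exposure part depends on whether the predicted absorption limit holds. The floor (1 or 5 mg) and duration (28 or 29 days) differences are minor and have no bearing on dosing above 300 mg. No view is taken here on which limit, floor or duration is right.

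**What to change.** Reconcile five places to a single ceiling rule: the synopsis (Treatment Arms, Part B), the Figure GSEA.1 note, both statements in Section 6.1.2, and Section 8.3.1. The rule should say whether it refers to the dose evaluated or the dose tolerated in Part A, and how any fixed mg limit combines with it. Then make sure that the benefit/risk statement in Section 4.3 and Table GSEA.1 cover whatever ceiling results. The value is for the sponsor's clinical team.

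In the same edit, state one floor in Section 6.1.2 and the figure note, and reconcile the duration in the Section 6.5 rationale with the dosing days given in the synopsis, Figure GSEA.1 and Sections 6.1.2 and 8.1.

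The cost is protocol wording, plus a margin calculation if the ceiling chosen lies outside the present table. Sample size and analysis methods are unaffected.

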6.2. Number of Participants

Eighteen healthy males and female subjects may be enrolled in Part A where each subject is scheduled to receive 2 single doses of LY3202328 and 1 dose of placebo in ascending dose levels. Forty subjects may be enrolled in Part B (8 subjects will receive LY3202328 and 2 subjects will receive placebo in each of 4 dose level cohorts). Additional subjects may be enrolled to replace drop-outs or discontinued subjects, but are not required. Replacement subjects may complete any portion of the study as needed, i.e. any portion not completed by the discontinued subject with the goal to complete up to 18 subjects in Part A and up to 40 subjects in Part B. The decision to replace subjects will be discussed with the Sponsor prior to adding subjects.

6.3. End of Study Definition

End of the study is the date of the last visit or last scheduled procedure shown in the Schedule of Events ([Appendix 2](#)) for the last subject.

6.4. Scientific Rationale for Study Design

The purpose of this study is to evaluate the safety, tolerability, PK, and degree of target inhibition (PD) of LY3202328 when administered orally as single doses to statin-free, overweight, healthy subjects (Part A) and as multiple doses (with a statin DDI assessment) to statin-free, overweight, dyslipidemic subjects (Part B).

For Part A, a standard single-dose, double-blind, randomized, placebo-controlled, SAD crossover design will be used. A randomization schedule for treatment sequence assignment will be used to reduce the potential for selection bias. For Part B, a double-blind, randomized, placebo-controlled, sequential MAD design will be used. The data obtained from this study will help establish the doses suitable for administration to patients with dyslipidemia and the possible existence of a DDI between LY3202328 and simvastatin and/or atorvastatin prior to studies in patient populations on stable treatment.

The selection of healthy subjects is appropriate and consistent with standard practices for an early phase clinical pharmacology study. The inclusion and exclusion criteria are chosen to select subjects who are known to be free from any significant illness. A placebo is included to enable characterization of AEs by serving as a negative control. LY3202328 is not anticipated to provide any benefit to the study subjects, and therefore the use of placebo will not deprive subjects of any benefit.

6.5. Justification for Dose

Human PK/PD modeling and preclinical absorption, disposition, metabolism, and excretion (ADME) profiles in rat, dog, and primate were used to predict that LY3202328 should achieve a sustained average ED₈₀ concentration in man with an oral dose of 13 mg QD. This projected human dose compares favorably with the projected maximum absorbable dose of 190 mg determined using GastroPlus modelling of rat, dog, and monkey ADME profiles. In chronic lipid lowering studies, LY3202328 produced dose-dependent inhibition of LDL-c (61%), ApoB (53%), ApoC3 (43%), and PCSK9 (55%) in plasma, as well as liver TG (37%) in LDLr KO mice, and reduced liver TG (56%) in C57Bl/6 mice on a high fat diet. Finally, body surface area dose and predicted AUC exposure multiples are greater than 195x in GLP rat and dog toxicology studies relative to the predicted efficacy dose/exposure, and greater than 13x relative to the highest planned human dose of 300 mg. The proposed dose range for this first-in man-study of 1 to 300 mg of LY3202328 administered orally QD for up to 28 days was selected based on toxicology studies and modeling of PK/PD data from nonclinical studies of LY3202328, and the established margin of safety.

The nonclinical no-observed-adverse-effect level (NOAEL) doses and AUC values for LY3202328 following daily administration compared with planned human doses and projected human exposures are presented in [Table GSEA.1](#).

Table GSEA.1. Margin of Safety for Oral Administration of LY3202328 Based on Administered Dose and Predicted Exposure

	Dose (mg)	Dose (mg/kg)	HED (mg/kg)	Dose Multiple ^a	AUC ($\mu\text{g}\cdot\text{h}/\text{mL}$) ^b	Exposure Multiple ^a
Human^c				—	—	—
Starting dose	1	0.0143	0.0143		0.6	
Efficacy dose	13	0.186	0.186		7.8	
Highest dose	300	4.29	4.29		114	
Rat NOAEL^d		500	80.6		1710	
Starting dose				5600x		2850x
Efficacy dose				433x		219x
Highest dose				19x		15x
Dog NOAEL^e	250	139			1520	
Starting dose				9700x		2533x
Efficacy dose				747x		195x
Highest dose				32x		13x

Abbreviations: AUC = area under the plasma concentration x time curve; HED = human equivalent dose based on body surface area; NOAEL = no-observed-adverse-effect level.

a Dose multiple is the dose in animal HED/human dose based on mg/kg² using Guidance for Industry, Estimating the Maximum Safe Starting Dose in Initial Clinical Trials for Therapeutics in Adult Healthy Volunteers, FDA/CDER, July 2005. Exposure multiple is the calculated as AUC in animals/predicted AUC in humans.

b Predicted human AUC over 24 hours upon repeat once daily dosing, based on predicted human pharmacokinetics mentioned in Section 5.1.8 of the Investigators Brochure. Note: human predicted AUC listed at a dose of 300 mg accounts for the expected absorption limitation, resulting in a maximum absorbable dose of 190 mg.

c Clinical dose based on 70-kg human.

d NOAEL determined in a 28-day repeat dose rat toxicity study. AUC is mean of male and female data at the end of the study (Study 8327-151).

e NOAEL determined in a 28-day repeat dose dog toxicity study. AUC is mean of male and female data at the end of the study (Study 8327-163).

7. Study Population

Eligibility of subjects for study enrollment will be based on the results of screening medical history, physical examination, vital signs, clinical laboratory tests, and ECG results.

The nature of any conditions present at the time of the physical examination and any preexisting conditions will be documented.

Prospective approval of protocol deviations to recruitment and enrollment criteria, also known as protocol waivers or exemptions, are not permitted.

